## 5 Descriptive Statistics

Unless otherwise specified, summary statistics (n, arithmetic mean, standard deviation [SD], median, lower and upper quartiles, minimum and maximum values) will be presented for continuous variables, and counts and, if relevant, percentages will be presented for categorical variables.

Furthermore, and unless otherwise specified, the data will be summarised for all patients, and by lead-in study and by lead-in treatment, respectively.

Lastly, and unless otherwise specified, data listings will include site, lead-in study, patient number, sex, age, race, and weight at OLEXA.

## 6 Patient Disposition

### 6.1 Summary of Patient Disposition

Patient disposition will be summarized for all patients and by lead-in studies, and will include the number of patients in each analysis set defined in chapter 4, and the number of patients in the APTS who completed or withdrew from study.

### 6.2 Withdrawals

The number of patients who withdrew will be summarized for all patients, by lead-in studies and by lead-in treatment, respectively, and by primary reason for withdrawal and all reasons for withdrawal.

Patients who withdrew will be listed and the listing will include the number of days in the study until withdrawal, the number of days on IMP, the primary reason for withdrawal and all reasons for withdrawal.

Kaplan-Meier plots of time to withdrawal will be presented for all patients, by lead-in studies and by lead-in treatment, respectively. The time will be calculated from the date of first dose of IMP in the current trial to the date of completion or withdrawal. Patients who completed study will be regarded as censored.

All tables, graphs, and listings will be based on the APTS.

## 7 Demographics and Baseline Characteristics

Demographics (sex, age, race); baseline (OLEXA) characteristics (height, weight, BMI and Tanner score); and baseline efficacy variables will be summarized for all patients and by lead-in study and by lead-in treatment when applicable.

Demographics and baseline characteristics will be summarized based on the APTS, and baseline efficacy variables will be summarized based on the FAS.

## 8 Recent and Concomitant Medication

Recent and concomitant medication will be coded using the *WHO Drug Dictionary* (WHO-DDE).

Medications will be classified according to the start and stop time and summarized by anatomical therapeutic chemical (ATC) code, generic drug name, for all patients and by lead-in study and by lead-in treatment, respectively:

- concomitant medication continued from lead-in studies
- concomitant medication started at or after Visit 1 of study 12712A

The tables will be based on the APTS.

## 9 Exposure and Compliance

Exposure (days) to IMP will be calculated as:

- Date of last dose of IMP – Date of first dose of IMP in study 12712A + 1

Exposure to IMP will be summarized for all patients and by lead-in study and by lead-in treatment using descriptive statistics, and, will include the patient years of exposure (PYE). PYE will be calculated as the sum of the number of days of exposure to IMP for each patient, divided by 365.25 days.

In addition, exposure to IMP will be categorized in intervals (1 – 14 days, 15 – 35 days, 36 – 70 days, 71 – 105 days, 106 – 140 days, 141 – 182 days and >182 – days) and summarized by lead-in study and by lead-in treatment. Missing values of exposure will not be imputed.

Non-compliant days are days on which no IMP has been taken, less than the full dose of IMP has been taken, or more than the full dose of IMP has been taken.

Compliance (%) with IMP will be calculated as:

- $(\text{date of Completion/Withdrawal Visit} - \text{date of Visit 1} - \text{number of days of non-compliance}) / (\text{date of Completion/Withdrawal Visit} - \text{date of Visit 1}) \times 100\%$

where the number of non-compliant days is defined as the sum of all non-compliant days in the treatment period.

Compliance with IMP will be categorized as “≤80% compliant” or “>80% compliant”. The number and percentage of patients in each category will be summarized by lead-in study and lead-in treatment, respectively, by visit interval and for the entire study.

The mean and modal dose of IMP will be calculated for each patient and summarised (mean, median, and lower and upper quartiles for the mean and counts for the modal dose). IMP dose level at the completion or withdrawal of the study will be summarized. Number and percentage of patients who reached highest and lowest dose level will be summarised. In addition, number and percentage of patients with each dose level will be summarised by visit.

Number of patients who exposed to oral drops will be summarized.

Exposure and compliance will be summarized based on the APTS.

## 10 Efficacy

### 10.1 Overview of Planned Efficacy Analyses

An overview of all planned efficacy analyses is provided in [Panel 2](#).

#### Panel 2 Overview of Planned Efficacy Analyses

	Endpoints	Description	Type
Depressive Symptoms	Change from OLEXA to week 26 in CDRS-R  total score		1
	Remission	Defined as CDRS-R $\leq$ 28	2
	Relapse	Defined as CDRS-R value $\geq$ 40	2
Global Clinical Impression	Change from OLEXA to week 26 in CGI-S score		1
	CGI-I score at week 26	In reference to Baseline A in the lead-in study	1
Cognitive Function	Change from OLEXA to week 26 in BRIEF (parent) using Global Executive Composite Score	For children (aged 7-11 years at OLEXA), 72 items are included in GEC	1
	Change from OLEXA to week 26 in BRIEF (parent) using Metacognition Index Score	For children (aged 7-11 years at OLEXA), 44 items are included in MI	1
	Change from OLEXA to week 26 in BRIEF-SR using Global Executive Composite Score	For adolescents (aged 12-18 years at OLEXA), 80 items are included in GEC	1
	Change from OLEXA to week 26 in BRIEF-SR using Metacognition Index Score	For adolescents (aged 12-18 years at OLEXA), 42 items are included in MI	1

Functionality	Change from OLEXA to week 26 in CGAS  score	1
	Change from OLEXA to week 26 in PedsQL  VAS score	1

1 = continuous; 2 = binary

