3.2 Rationale for the Study Design

The proposed study 12712A is an interventional, open-label, flexible-dose, long-term extension study with the primary objective to evaluate the long-term safety and tolerability of vortioxetine in children and adolescents with a DSM-5™ diagnosis of MDD who completed studies 12709A or 12710A. Secondary objectives are to evaluate the long-term effectiveness of flexible doses of vortioxetine in a range of 5 mg/day to 20 mg/day on depressive symptoms, clinical global impression, cognitive function and functionality.

In the overall adult clinical development programme, treatment with vortioxetine at the therapeutic doses (5-20 mg/day) was safe and well tolerated. It has been suggested that a failure to conduct and use information from appropriately designed preliminary pharmacokinetic and dose-finding studies has contributed to the failure of several large scale antidepressant studies in the paediatric MDD population.²¹ The chosen doses of vortioxetine for this study are based on the knowledge from the clinical development programme in adult patients and from the paediatric pharmacokinetic and tolerability study performed in the paediatric population (aged 7 to 17 years) designed to guide the choice of doses to be used in the planned paediatric investigation plan.

The primary efficacy endpoint will be the CDRS-R total score. The CDRS-R²² is the most widely used rating scale in clinical trials for assessing severity of depression and change in depressive symptoms in children and adolescents with depression. The CDRS-R is based on the adult Hamilton Depression Rating Scale. The Psychometric analyses provide evidence that the CDRS-R is a valid measure of severity and improvement of depressive symptoms in paediatric patients. A score of ≥ 40 is indicative of depression, whereas a score ≤ 28 is often used to define remission (minimal or no symptoms).

The CGI-S and CGI-I will be used for assessing disorder severity and improvement.²³

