16.2 Secondary Endpoints

Depressive symptoms:

- change from Baseline Extension A to Week 26 in CDRS-R total score
- time to first relapse (CDRS-R value of ≥ 40)
- time to first loss of remission (CDRS-R > 28)

Global Clinical Impression:

- change from Baseline Extension A to Week 26 in CGI-S score
- CGI-I score at Week 26. The assessment of the CGI-I should be in reference to Baseline A in the lead-in studies.

Cognitive function:

Children (7-11 years)

- change from Baseline Extension A to Week 26 in BRIEF using the Global Executive Composite score
- change from Baseline Extension A to Week 26 in BRIEF using the Metacognition Index

Adolescents (12-18 years)

- change from Baseline Extension A to Week 26 in BRIEF-SR using the Global Executive Composite score
- change from Baseline Extension A to Week 26 in BRIEF-SR using the Metacognition Index

Functionality:

- change from Baseline Extension A to Week 26 in CGAS score
- change from Baseline Extension A to Week 26 in PedsQL VAS

17 Statistical Methodology

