## **4 Analysis Sets**

The following analysis sets will be used to analyse and present the data:

- all-patients-treated set (APTS) – all patients who took at least one dose of vortioxetine in 12712A.
- full-analysis set (FAS) – all patients in the APTS with valid OLEXA assessment and at least one valid post-OLEXA assessment of the CDRS-R total score.

The safety analyses will be based on the APTS. The efficacy analyses will be based on the FAS.

The patients and data will be classified into the analysis sets according to the definitions above after the study database has been released.

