## 10.2 General Efficacy Analysis Methodology

Unless otherwise specified, all the efficacy analyses will be based on the FAS.

All the tables and graphs will be presented for all patients and by lead-in studies and by lead-in treatments, respectively.

Analysis of the endpoints subjected to inferential statistical methods will be presented with 95% CIs.

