## 10.3 Analysis Methodology for the Secondary Endpoints

### 10.3.1 Analysis of the Secondary Endpoints

Absolute values and change from OLEXA in the continuous efficacy variables, except CGI-I, will be summarized descriptively. Absolute values of CGI-I will be summarized.

CDRS-R remission and relapse during treatment period will be summarized descriptively by visit.

For the continuous efficacy variables CDRS-R and CGI-S, change from OLEXA will be analyzed using a restricted maximum likelihood (REML)-based Mixed Model Repeated Measurements (MMRM) approach, using all available observations until completion or withdrawal.

The model will include country, lead-in study interacting with week as factors, and baseline score interacting with week as covariate. An unstructured covariance structure will be used to model the within-patient errors and the Kenward-Roger approximation will be used to estimate denominator degrees of freedom.

For the CDRS-R total score the primary analyses will be also presented by lead-in study by lead-in treatment.

In addition, ANCOVA models will be fitted for CDRS-R and CGI-S, including country and lead-in study as factors and baseline score as a covariate, the analysis will be conducted by visit, based on OC and LOCF.

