## 17 Changes to Analyses Specified in the Protocol

The following changes have been made as compared to the latest version of the protocol:

- C-SSRS categorisation has been updated and will no longer include C-CASA.
- Treatment emergent adverse events (TEAE) in 12712A is defined as an adverse event that starts or increases in intensity or seriousness after visit 1 of study 12712A.
- The analyses regarding time to first relapse and time to first loss of remission have been removed
- The analysis of random slope and intercept has been removed

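### SAP Panel 2 defines relapse as any CDRS-R score of 40 or more, with no condition on an earlier score, so patients who enter at 40 or more and never fall below it are counted as relapses

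*SAP*

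**What the plan says.** SAP Panel 2 gives the relapse endpoint one line, "Defined as CDRS-R value $\geq$ 40", and types it as binary. SAP 10.3.1 gives the analysis: "CDRS-R remission and relapse during treatment period will be summarized descriptively by visit". It names no at-risk group and no denominator.

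SAP 10.2 supplies the defaults. On population: "Unless otherwise specified, all the efficacy analyses will be based on the FAS". On layout: "All the tables and graphs will be presented for all patients and by lead-in studies and by lead-in treatments, respectively". SAP section 4 defines the FAS as "all patients in the APTS with valid OLEXA assessment and at least one valid post-OLEXA assessment of the CDRS-R total score". It requires an OLEXA score but sets no limit on its value.

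Protocol 16.2 has time to first relapse as a secondary endpoint, with the same bare threshold of 40. SAP section 17 withdraws the time-to-event versions: "The analyses regarding time to first relapse and time to first loss of remission have been removed". It adds no condition to the relapse definition, so the by-visit table is the only relapse output left. Protocol 3.2 says what the cut-offs mean: "A score of ≥ 40 is indicative of depression, whereas a score ≤ 28 is often used to define remission".

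**The concern.** A score of 40 or more describes a state at one visit. Relapse is a change from a better state to a worse one. Without a condition on an earlier score, the definition cannot separate patients who worsened from patients who were unwell on entry and stayed so. It also counts as relapsed a patient who has improved but is still at 40 or more.

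A table headed relapse would then mix persistent illness with worsening, and it may be quoted as a relapse rate. Because it is also shown by lead-in treatment, a difference between groups in the share entering at 40 or more could look like a difference in relapse.

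**Working it through.** **Can a patient enter at 40 or more?** Yes. In protocol 5.2, inclusion criterion 7 requires completion of the lead-in study and criterion 9 requires the investigator's opinion that long-term treatment is indicated. No inclusion or exclusion criterion sets a response, remission or CDRS-R threshold. The enrolment figure agrees with this, since it applies acceptance of at most 85% to all lead-in completers, with no responder filter:

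- 15% lead-in withdrawal: 1200 × 0.85 × 0.85 = 867
- 20% lead-in withdrawal: 1200 × 0.80 × 0.85 = 816

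These bracket the stated figure of approximately 850. The documents give no figure for relapse to reproduce.

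**What does the rule count?** The table takes five invented score paths, read at the last visit shown, under Panel 2 and under two possible conditions.

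| OLEXA, then later scores | Panel 2 | Only if OLEXA <40 | Only if any earlier score <40 |
|---|---|---|---|
| 45, 45 | relapse | no | no |
| 55, 50 | relapse | no | no |
| 30, 45 | relapse | relapse | relapse |
| 55, 25, 45 | relapse | no | relapse |
| 39, 40 | relapse | relapse | relapse |

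Panel 2 is wrong on the first two rows. A condition on OLEXA alone corrects those but loses the fourth patient, who reached remission on study and then returned to 40 or more. A condition on any earlier score handles all four. The last row shows what neither condition settles: a score of 39 is not remission, and a one-point move still counts.

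**How large could the effect be?** The inputs are not in the documents, so all are assumed:

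- p, the share at 40 or more at OLEXA: 0.10 to 0.50
- r, the share of those at 40 or more at a given visit: 0.30 to 0.80
- q, the share of the others at 40 or more at that visit: 0.05 to 0.10

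The labelled relapse rate is L = p·r + (1 − p)·q. The share of labelled patients already at 40 or more at entry is p·r / L.

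- Lowest (p = 0.10, r = 0.30, q = 0.10): L = 0.03 + 0.09 = 0.12; share = 0.03 / 0.12 = 25%; L / q = 1.2
- Middle (p = 0.30, r = 0.50, q = 0.075): L = 0.15 + 0.0525 = 0.2025; share = 0.15 / 0.2025 = 74%; L / q = 2.7
- Highest (p = 0.50, r = 0.80, q = 0.05): L = 0.40 + 0.025 = 0.425; share = 0.40 / 0.425 = 94%; L / q = 8.5

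The direction needs only p > 0 and r > q, because L − q = p·(r − q). The size depends wholly on the assumptions. The product p·r also includes patients who fell below 40 and came back, so the share already at 40 or more at entry is an upper limit on the share who never fell below it.

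**Could entry severity show up as a treatment difference?** If two lead-in groups had the same r = 0.50 and q = 0.075 but entered with p = 0.20 and p = 0.30, the labelled rates would be 0.10 + 0.06 = 16.0% and 20.25%. That is a gap of 4.25 percentage points with no difference in persistence or in new crossings. The documents do not show that the groups differ at entry.

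**The case against.** The case for leaving the row alone is that the cut-off is stated openly and carried over from the protocol. The output is a descriptive count in an overview panel, and SAP 3.2 does not list relapse as an endpoint. A reader can see entry scores by lead-in study and treatment under SAP section 7, and can see absolute CDRS-R and change from OLEXA under 10.3.1. The MMRM and ANCOVA adjust for the baseline score. The SAP also relies on a separate Data Handling Plan, which was not available for this review.

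Most of that stands, and it is why the point is minor. It does not rescue the label. Agreement with the protocol means the problem was carried over, not that it is absent. Separate entry summaries let a reader suspect the mixture but do not correct the count. The SAP cites the Data Handling Plan for other matters, such as adverse event phases and the windowing of visits, but not for relapse.

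Two further objections stand. First, the simplest remedy, reserving relapse for patients with OLEXA below 40, would drop a patient who enters at 55, falls to 25 and returns to 45. The condition therefore has to look at any earlier score. Second, a threshold of 40 on the earlier score does not require remission, and the documents do not say which earlier state a relapse should start from.

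**Conclusion.** The point holds as a minor error of definition. As written, the row gives the proportion with CDRS-R of 40 or more at each visit, and it counts as relapses patients who entered at that level and never fell below it. This follows from the text alone: the Panel 2 definition, an FAS with no limit on the OLEXA score, and selection criteria with no CDRS-R threshold.

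A reader might infer three stronger things, none of which the documents support.

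- *Most counted relapses are false.* The 25% to 94% range comes entirely from assumed inputs and is not evidence of size. It also describes status at entry, not whether a patient stayed at 40 or more throughout.
- *The display by lead-in treatment is biased.* It could be, if the share at 40 or more at OLEXA differs between groups. Nothing in the documents shows that it does.
- *The trial's main results are affected.* They are not. The primary endpoint is safety, the relapse table is descriptive, and the CDRS-R and CGI-S models do not use the relapse variable.

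**What to change.** In SAP Panel 2 and 10.3.1:

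1. Label the all-FAS by-visit row 'CDRS-R ≥40' and split it by OLEXA status (<40 and ≥40). Use as denominator the number of patients with a CDRS-R value at that visit.
2. If the term relapse is kept, apply it only to a value of 40 or more in a patient with an earlier value below 40, at OLEXA or at a previous post-OLEXA visit. The at-risk denominator at each visit is then the patients with a value at that visit and at least one earlier value below 40. Show it in the table.
3. List the change in SAP section 17, because the protocol uses the threshold without a condition.

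The cost is a few lines of SAP text and one extra table split. No new data are needed, because every FAS patient has a valid OLEXA score. The relapse denominator becomes smaller. At the first post-OLEXA visit it is 1 − p of the patients with a value, or 50% to 90% under the assumed p of 0.50 to 0.10, and patients who later fall below 40 join it.

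One limit remains. SAP 18.4 records that before protocol amendment PA2 the CDRS-R was assessed only at weeks 0, 12 and 26. Some improvements below 40 between those visits will not be seen in those patients, and a footnote should say so.

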## 10.2 General Efficacy Analysis Methodology

Unless otherwise specified, all the efficacy analyses will be based on the FAS.

All the tables and graphs will be presented for all patients and by lead-in studies and by lead-in treatments, respectively.

Analysis of the endpoints subjected to inferential statistical methods will be presented with 95% CIs.

## 10.3 Analysis Methodology for the Secondary Endpoints

### 10.3.1 Analysis of the Secondary Endpoints

Absolute values and change from OLEXA in the continuous efficacy variables, except CGI-I, will be summarized descriptively. Absolute values of CGI-I will be summarized.

CDRS-R remission and relapse during treatment period will be summarized descriptively by visit.

For the continuous efficacy variables CDRS-R and CGI-S, change from OLEXA will be analyzed using a restricted maximum likelihood (REML)-based Mixed Model Repeated Measurements (MMRM) approach, using all available observations until completion or withdrawal.

The model will include country, lead-in study interacting with week as factors, and baseline score interacting with week as covariate. An unstructured covariance structure will be used to model the within-patient errors and the Kenward-Roger approximation will be used to estimate denominator degrees of freedom.

For the CDRS-R total score the primary analyses will be also presented by lead-in study by lead-in treatment.

In addition, ANCOVA models will be fitted for CDRS-R and CGI-S, including country and lead-in study as factors and baseline score as a covariate, the analysis will be conducted by visit, based on OC and LOCF.

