- Analyses of safety endpoints:
 - Adverse events, PAERS items, Tanner scores, clinical safety laboratory tests, vital signs, height, weight, BMI, and ECG parameters will be summarised, and observed potentially clinically significant (PCS) safety laboratory test values will be flagged and summarised. The length of menstrual cycle and C-SSRS scores will be summarised using descriptive statistics.
 - The change from baseline will be derived with respect both to baseline in the lead-in studies and baseline in extension Study 12712A.
- The primary objective will be addressed with an overall clinical evaluation of the safety results.
- Adverse events occurring in the first two weeks of the study will be reported separately.
- The efficacy analyses will be based on the FAS.
- Analyses of efficacy endpoints:
 - Change from Baseline Extension A in CDRS-R, CGI-S, BRIEF, CGAS, and PedsQL VAS using descriptive statistics by lead-in study and by lead-in treatment.
 - CGI-I score at week 26 using descriptive statistics by lead-in study and by lead-in treatment.
 - Time to first relapse (CDRS-R value of ≥ 40) using Kaplan-Meier estimates.
 - Time to first loss of remission (CDRS-R > 28) using Kaplan-Meier estimates.
- For exploratory use a random effects slope and intercept model on safety and efficacy parameters will be applied using Mixed Model Repeated Measurements (MMRM) to study long-term development in safety and efficacy parameters (e.g. weight and CDRS-R).
- Summaries and analyses will be performed with respect to the Baseline in the lead-in studies.
- No interim analyses for efficacy are planned. A DMC will monitor safety data at regular intervals to be specified in the Data Monitoring Committee Charter.

Pharmacokinetic Analysis

Sparse PK samples (2) will be collected to measure vortioxetine plasma concentration. The population PK of vortioxetine will be assessed by means of nonlinear mixed effect modelling and the results from the analysis will be reported in a separate population PK report.

Sample Size Considerations

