17.8 Efficacy Analyses

17.8.1 General Efficacy Analysis Methodology

Change from Baseline Extension A in CDRS-R, CGI-S, BRIEF, CGAS, and PedsQL VAS using descriptive statistics by lead-in study and by lead-in treatment.

CGI-I score at Week 26 using descriptive statistics by lead-in study and by lead-in treatment.

Time to first loss of remission and time to first relapse will be analysed using Kaplan-Meier estimates.

For exploratory use a random effects slope and intercept model will be applied using Mixed Model Repeated Measurements (MMRM) to study long-term development in efficacy parameters such as CDRS-R.

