17.10.2 Analyses of Safety Endpoints

Adverse events, PAERS items, Tanner scores, clinical safety laboratory tests, vital signs, height, weight, BMI, and ECG parameters will be summarised, and observed potentially clinically significant (PCS) safety laboratory test values will be flagged and summarised. Length of menstrual cycle and C-SSRS scores will be summarised using descriptive statistics.

For variables that are heavily dependent on sex and age (such as Tanner and menstrual cycle length) further exploratory descriptions will be made.

Analyses will be performed with respect to the baseline in lead-in study 12709A or 12710A and Baseline Extension A.

For exploratory use a random effects slope and intercept model will be applied using Mixed Model Repeated Measurements (MMRM) to study long-term development in safety parameters such as weight.

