## **Appendix III**

### **SAS® Code**

## SAS® Code

### MMRM for analysing continuous endpoints

```
proc mixed noclprint data=xyz ic method=reml;  
  class usubjid country week lead-in _study;  
  model y=baseline country week lead-in_study*week baseline*week / s ddfm=kr;  
  repeated week/subject=usubjid type=un;  
  run;
```

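### Apart from CGI-I, SAP efficacy change is taken only from the post-lead-in baseline (OLEXA), and the CDRS-R model as coded cannot give the results promised by lead-in treatment

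*SAP*

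**What the plan says.** **Efficacy reference point.** SAP 3.2 and Panel 2 define the change endpoints from OLEXA to Week 26, and SAP 10.3.1 follows: "Absolute values and change from OLEXA in the continuous efficacy variables, except CGI-I, will be summarized descriptively". For scales used in the lead-in studies, OLEXA is the lead-in completion visit (SAP 18.1); SAP 3.2 places lead-in Baseline A 12 weeks before it. CGI-I is rated against Baseline A. SAP 10.2 presents all efficacy tables by lead-in study and by lead-in treatment.

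**Safety reference point.** SAP 12.2 uses both the lead-in baseline and OLEXA.

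**Protocol.** Under safety, the synopsis says: "The change from baseline will be derived with respect both to baseline in the lead-in studies and baseline in extension Study 12712A". Further down, after the efficacy and exploratory bullets, a separate bullet says: "Summaries and analyses will be performed with respect to the Baseline in the lead-in studies". In the body, 17.8.1 specifies "Change from Baseline Extension A in CDRS-R, CGI-S, BRIEF, CGAS, and PedsQL VAS using descriptive statistics by lead-in study and by lead-in treatment", and 16.2 likewise uses Baseline Extension A. The lead-in baseline is named for analysis only in the safety section, 17.10.2: "Analyses will be performed with respect to the baseline in lead-in study 12709A or 12710A and Baseline Extension A".

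**Declared changes.** SAP 17 opens with "The following changes have been made as compared to the latest version of the protocol" and lists four items: C-SSRS categorisation, the TEAE definition, removal of the two time-to-event analyses, and removal of the random slope and intercept model. The efficacy reference point is not among them.

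**Model.** The code in SAP Appendix III has "model y=baseline country week lead-in_study*week baseline*week", which matches the text of 10.3.1. Lead-in treatment is in neither. SAP 10.3.1 nevertheless promises: "For the CDRS-R total score the primary analyses will be also presented by lead-in study by lead-in treatment".

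**The concern.** There are two separate problems.

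The first is the reference point. OLEXA comes at the end of a double-blind, placebo-controlled, active-reference treatment period. If the arms separated during that period, the groups enter the extension at different levels. A group that improved early and held its gain then shows a change near zero, and a group that improves late shows a large change. A reader comparing change scores across lead-in treatments could take the second as a better long-term result. Two features add to this. CGI-I and CGI-S change are reported side by side with different time origins. The Kaplan-Meier analyses of relapse and loss of remission, which spoke directly to maintenance, have been removed.

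The second is the model. Results by lead-in treatment are promised from a model that does not contain lead-in treatment, and the code has no BY or LSMEANS statement. Whoever programs it must choose between separate fits and an added term. The two choices answer different questions and can give different numbers.

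**Working it through.** **1. The plan's own figure.** The only planning number is about 850 patients (protocol 17.12, SAP 15): 1200 randomised, 15-20% withdrawal, at most 85% continuing.
- 1200 × 0.85 × 0.85 = 867
- 1200 × 0.80 × 0.85 = 816

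The stated 850 lies in this range. It is used below only for cell sizes.

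**2. The texts side by side.**

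| Place | Safety | Efficacy change |
|---|---|---|
| Protocol synopsis | both baselines | extension baseline, then an unscoped bullet naming lead-in baseline |
| Protocol body (16.2, 17.8.1, 17.10.2) | both baselines | extension baseline; CGI-I against Baseline A |
| SAP (3.2, 10.3.1, 12.2) | both baselines | OLEXA; CGI-I against Baseline A |

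Safety already has its own sentence in the synopsis, so the later bullet adds nothing unless it reaches beyond safety. The protocol body does not repeat it for efficacy. The protocol is therefore not consistent with itself, and the SAP does not settle the point.

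**3. What the choice of baseline does.** Let A, O and W be a group's means at lead-in Baseline A, OLEXA and Week 26. Then W − A = (O − A) + (W − O). The between-group contrast in W − O equals the contrast in W minus the contrast in O. A gap of d at OLEXA therefore enters the contrast in full.

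Illustration, all values assumed and chosen so that the totals agree:

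| Lead-in group | O − A | W − O | W − A |
|---|---|---|---|
| ex-vortioxetine | −25 | −4 | −29 |
| ex-placebo | −20 | −9 | −29 |

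Change from OLEXA differs by 5 points; change from Baseline A does not differ.

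**4. What an added model term does.** Suppose the groups share A and W means, differ by d at OLEXA, and the within-group slope of Week 26 score on OLEXA score is b. Separate fits, each evaluated at its own OLEXA mean, give a contrast of d. One model with a treatment term gives d − (1 − b)d = b·d. A simulation with a single Week 26 outcome (100,000 per group, assumed b of 0.3, 0.5 and 0.7) agrees:

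| d | change from OLEXA, and separate fits | change from Baseline A | one model with term (b = 0.3 / 0.5 / 0.7) |
|---|---|---|---|
| 0 | −0.08 to 0.00 | −0.13 to 0.00 | 0.02 / −0.03 / −0.09 |
| 2 | 1.99 to 2.03 | −0.05 to 0.08 | 0.60 / 1.01 / 1.42 |
| 4 | 3.99 to 4.13 | −0.04 to 0.02 | 1.28 / 2.06 / 2.78 |
| 6 | 6.00 to 6.05 | −0.04 to 0.11 | 1.82 / 3.05 / 4.20 |

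The two ways of fitting differ by (1 − b)d, so the SAP needs to say which is meant. Neither replaces change from Baseline A.

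**5. Feasibility of separate fits.** A placebo-controlled, active-reference design has at least 3 arms, so 2 studies give at least 6 cells, averaging at most 850/6 ≈ 142 patients. CDRS-R has 7 post-OLEXA visits (Weeks 1, 2, 4, 8, 12, 18, 26), so each unstructured matrix has 7 × 8/2 = 28 parameters; six fits need 6 × 28 = 168. Before the second protocol amendment CDRS-R was taken only at Weeks 0, 12 and 26 (SAP 18.4), so the other visits are sparser. With 3 arms per study, one model needs 2 × (3 − 1) × 7 = 28 extra fixed effects and keeps one 28-parameter matrix.

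**6. Effect on the overall estimate.** Assume 30% ex-placebo, withdrawal of 25-35% in that group against 15% in the others, and a 3-5 point difference in extension change. The ex-placebo share among completers moves as follows:
- 25%: 0.225/(0.225 + 0.595) = 0.274, a shift of 0.026; × 3 points ≈ 0.08
- 35%: 0.195/(0.195 + 0.595) = 0.247, a shift of 0.053; × 5 points ≈ 0.27

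Those are completers-only figures. An MMRM recovers part of the loss through earlier visits: a simulation of 850 patients, 7 visits and 300 replicates over assumed inputs of this kind gave biases of 0.05, 0.13 and 0.19 points without the term, and 0.00 to 0.02 with it.

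**The case against.** The strongest reply is that the SAP follows the protocol's specified endpoints. Synopsis endpoints, 16.2 and 17.8.1 all take efficacy change from Baseline Extension A. The unscoped bullet comes directly after the exploratory slope model, and if it belongs to that model, its removal is declared in SAP 17. SAP 17 may also refer to a protocol later than the one supplied: the SAP has an oral-drops palatability objective that this protocol lacks and that is not listed as a change. All of this stands. A reader might infer that the SAP silently broke a clear protocol commitment; the documents support only an ambiguity left unaddressed.

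Next, the starting points are not hidden. OLEXA efficacy values are tabulated by lead-in treatment where applicable (SAP 7), absolute values accompany change, and remission and relapse are summarised by visit. This stands too, and it rules out the inference that the tables must mislead. What remains missing is change from lead-in baseline in the patients who continued.

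Finally, everyone receives vortioxetine, safety is primary, no contrast between lead-in treatments is planned, and subgroup fits would be a natural way to meet the promise. Subgroup fits are a possible reading. But the SAP does not state it, `lead-in_study*week` is redundant within a single study, and the cells are small for the covariance structure.

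**Conclusion.** The point holds in a limited form. Apart from CGI-I and absolute values, efficacy is read from a baseline that 12 weeks of lead-in treatment may have moved. The distortion in change-score contrasts by lead-in treatment equals the OLEXA gap d, whatever d is; the documents give no OLEXA means, so its size is unknown and the 5-point example is only an illustration. The model as coded does not produce the promised CDRS-R results by lead-in study and treatment.

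Two stronger readings are not supported. A reader might infer that the missing model term causes the different starting points; they come from using OLEXA, and adding the term still leaves b·d. A reader might also infer that the overall Week 26 estimate is materially biased; on assumed inputs the bias is 0.05 to 0.2 points on a scale the protocol gives as 17 to 113.

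Neither change below restores a randomised comparison. Only lead-in completers who choose to continue are enrolled, and a model adjusted for OLEXA conditions on a post-randomisation score. This is worth correcting because it is cheap and makes maintained benefit readable; it does not touch the primary safety objective.

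**What to change.** 1. In SAP 10.3.1, add descriptive change from lead-in Baseline A, by visit and at Week 26, for CDRS-R, CGI-S, CGAS and PedsQL VAS where the scale was collected at lead-in baseline, overall and by lead-in treatment. BRIEF stays out: the flow chart does not mark it as carried over from the lead-in. Add a line in SAP 17 saying how the synopsis bullet has been read for efficacy.
2. For the CDRS-R results by lead-in treatment, add lead-in treatment within lead-in study, and its interaction with week, to the MMRM text and the Appendix III code, with the statement that produces the estimates.
3. Label those estimates as descriptive, for the two reasons given in the verdict.

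Cost: some wording, extra table columns, and a modest number of model parameters (28 fixed effects if each lead-in study has three arms). No new data are needed where the scales were collected in the lead-in; SAP 12.2 already links to lead-in baseline for safety.
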